VNS and PD: VNS is FDA approved for treatment-resistant epilepsy and depression. The vagus nerve does not have direct connections to cortical regions but rather sends projections through brainstem nuclei, which then relay signals to upper cortical regions. One of these brainstem nuclei used as a relay site is the locus coeruleus (LC), which contains noradrenergic (NA) neurons.¹ VNS increases NA concentrations in the prefrontal cortex of rats, NA neuronal firing rate in LC,² as well as brain derived neurotrophic factor (BDNF) expression in the cortex and hippocampus.³ The loss of LC-NA neurons is significant in PD⁴ and occurs earlier in the disease process than the loss of substantia nigra dopamine (SN-DA) neurons.^{5,6} Additionally, SN-DA neurons become more sensitive to various insults in the absence of NA nerve fibers.^{7,8} NA depletion itself has been implicated in a multitude of pathophysiologic mechanisms in PD, and includes gait dysfunction, dysautonomia, depression, apathy, inattention, and sleep disturbance.⁹

Preliminary data from our neuroscience laboratory (PI-[name]) shows that stimulating the vagus nerve for two weeks improved motor function and resulted in neurorestorative effects on DAergic and NAergic systems, and reduced cellular expression of alpha-synuclein¹⁰ in DA/NA double-lesioned rats. In addition, VNS resulted in a significant increase in BDNF levels in the target regions of the DA and NA neurons. VNS has also been shown to produce an anti-inflammatory effect by decreasing pro-inflammatory cytokines, increasing anti-inflammatory cytokines, and reducing gliosis in models of PD.¹⁰ These results provide pre-clinical evidence for VNS as a potential treatment strategy for PD patients; potentially addressing neuronal damage as well as motor and non-motor symptoms of the damaged noradrenergic and dopaminergic pathways.

Transcutaneous auricular VNS (taVNS): Although cervical VNS is relatively safe, the risks involved in surgical implantation as well as its high cost (about \$30-50k) make it less appealing and less available as a study modality. Recently, it has been shown that VNS can be administered non-invasively through stimulating the auricular branch of the vagus nerve located in the ear¹¹⁻¹³ with a transcutaneous electrical nerve stimulation (TENS) device. Our collaborators ([name] et al.) in the MUSC Brain Stimulation Lab conducted initial safety and feasibility trials of transcutaneous auricular VNS (taVNS) in healthy adults. In these studies, there were no adverse effects of taVNS observed. Their work validates ideal parameters for delivering taVNS, suggesting that one-minute taVNS periods at 200% perceptual threshold delivered at 500 μ s 25Hz are safe and tolerable and produce regional brain changes consistent with activating the vagus nerve related brain regions involved in neuroplasticity.¹³ The same group developed and conducted a concurrent taVNS/fMRI trial and demonstrated that the neurobiological effect of taVNS mimics that of cervically implanted VNS and targets several cortical and subcortical vagus afferent pathway targets. It additionally suggested that taVNS for short time periods activates the vagus nerve (10-25Hz, average 1.8mA). No rapidly accelerated or sustained drops

in HR were seen during the one-minute taVNS stimulation periods. A follow-up study determined that the optimal parameter to modulate the parasympathetic response via taVNS was 500µs pulse width, 10 & 25Hz for 60s duration.¹³

The significance of this study lies in the novelty of stimulating the vagus nerve non-invasively, in order to increase LC-NA neuronal firing and BDNF, and to decrease neuroinflammation. Given the absence of side effects in our human pilot study, we are hopeful to explore a well tolerated treatment option with potential for neuroprotective as well as symptomatic benefits in PD.

2. Objectives

The primary objective of the study is to examine the effect of taVNS on motor symptoms in patients with mild to moderate motor symptoms of PD. The study design is a single site, parallel, randomized, sham controlled, double blinded study, administering taVNS vs sham stimulation 5 days a week for 2 weeks to 35 study subjects. Additional outcomes will be effects on cognition, safety assessments, as well as stimulation effects on relevant biomarkers.

Specific Aim 1: To examine in a 2-week, randomized, sham controlled, double blind trial the effect of taVNS on motor symptoms in patients with mild to moderate motor symptoms of PD.

Hypothesis: taVNS will be superior to sham stimulation on its effects on the motor section of the Movement Disorder Society Unified Parkinson's Disease Rating Scale (MDS UPDRS; primary outcome measure).

Specific Aim 2: To examine in a 2-week, randomized, sham controlled, double blind trial the effect of taVNS on cognitive symptoms in PD.

Hypothesis: taVNS will be superior to sham stimulation on its effects on a composite score of the following cognitive assessment tools: DKEFS, Stroop, Digit symbol, Digit span forward and backwards, Fixation (control), Reflexive, and saccade inhibition tasks, CAARS, PROMIS (secondary outcome measure).

Specific Aim 3: To assess safety and tolerability of taVNS in PD.

Hypothesis: Treatment with taVNS will be as well tolerated as sham stimulation on the following parameters: acute monitoring of vital signs, MDS UPDRS motor evaluations and cognition testing to evaluate for worsening PD severity, adverse events or serious adverse events assessments, and the Columbia Suicide Severity Rating Scale (CSSRS). (tertiary outcome measure)

Specific Aim 4:(exploratory aim) To evaluate effects of taVNS versus sham stimulation on biomarkers relevant to VNS neurobiology.

Hypothesis: taVNS and not sham stimulation will lead to a decrease in serum inflammatory biomarkers (TNF-alpha, and IL-6), increase in serum BDNF, and increase in resting pupil diameter.

3. Design

Overview:

This pilot study of taVNS in PD intends to prove basic concepts of acute motor and cognition improvements with taVNS in PD patients. We will accomplish this by a two-week, single site, parallel, randomized, double blinded, sham-controlled pilot study of taVNS in 35 PD patients. There will be 1 screening visit, 10 stimulation visits, and 1 follow up visit.

At the **screening visit** (visit SC) we will obtain informed consent, review inclusion and exclusion criteria, medical history, demographics. We will obtain a baseline MoCA exam, based on proposed exclusionary criteria. For those enrolled, medications used in the treatment of PD will be held constant throughout the study. Baseline blood draw in the amount of 3 teaspoons (<15ML) for biomarkers will be obtained by appropriately trained personnel. Urine pregnancy test will be administered to women of childbearing potential. We will randomize the patient to sham (n=15) versus active taVNS stimulation (n=15), and obtain baseline cognition battery (in normal *ON PD medication state*) at this time.

At **visit 1**, MDS UPDRS motor evaluation will be videotaped in the *OFF PD medication state* (defined as at least 12 hours without PD medication). Stimulation or sham will occur over 1 hour as defined below, and then repeat MDS UPDRS motor evaluation will be videotaped. A blinded rater will later score the modified (minus rigidity) MDS UPDRS on all videos at completion of the study.

Visits 2-4 are stimulation treatment visits in the *ON med state* with safety assessments, but no efficacy measures.

Visit 5 (study mid point) includes *OFF med* motor evaluation pre/post stimulation as at visit 1, in addition to the stimulation session.

Visit 6 is a taVNS treatment visits in the *ON med* state with additional behavioral saccade testing.

Visits 7-8 are stimulation treatment visits in the *ON med state* with safety assessments, but no efficacy measures.

Visit 9 is an *ON med* stimulation visit, and includes repeat cognition battery following the stimulation session.

Visit 10 (final day of stimulation) includes *OFF med* motor evaluation pre/post stimulation as at visit 1, in addition to the stimulation session. Repeat blood draw.

Visit 11 (Safety follow up visit) six to fourteen days after visit 10, we will check for any adverse events that might have occurred since the last stimulation session.

SCHEDULE OF ACTIVITIES

	Screening Baseline			Maintenance Phase					Follow up
	Visit SC Week 0-2 (-14d)	Visit 1 Stim day 1	Visit 2-4	Visit 5	Visit 6	Visit 7-8	Visit 9	Visit 10	+6-14 days
Written Informed Consent	x								
Eligibility Criteria	x								
MoCA	x								
Med/Neuro History	x								
Physical Exam	x								x
Blood Draw	x								
Cognitive Battery	x						x		
C-SSRS	x				x		x		
Pre-stim MDS UPDRS		x		x					x
stimulation thresholds		x							
taVNS vs sham stimulation		x	x	x	x	x	x	x	
pupillometry		x							
saccade					x				
Vital Signs		x	x	x	x	x	x	x	
Post-stim MDS UPDRS		x		x				x	
Monitoring AE		x	x	x	x	x	x	x	x

MDS-UPDRS- Movement Disorder Society- Unified Parkinson's Disease Rating Scale (motor portion used)

C-SSRS- Columbia-Suicide Severity Rating Scale

[figure not shown]
taVNS- transauricular vagal nerve stimulation

saccade- Fixation (control), Reflexive, and saccade inhibition tasks. This is INCLUDED in cognitive battery, but will be done as a stand-alone test on stim day 6

Cognitive Battery- DKEFS, Stroop test, Digit-Symbol test, Digit Span, saccade,

Patient reported measures- CAARS, PROMIS (fatigue, sleep related, Applied Cognitive Abilities)

Figure 1: Overview of Study Flow / Assessments

4. Eligibility Criteria

Inclusion Criteria:

Age: 40-82 y
Idiopathic Parkinson's Disease Diagnosis
Disease Stage: Hoehn and Yahr stage 2-3
Patient requires a minimum of 3 doses of levodopa daily
Willingness to be videotaped

Exclusion criteria:

Dementia or MoCa <24
PD psychosis
Ear trauma
Facial pain
TBI or clinical history of stroke
Metal implants above the shoulders
History of myocardial infarction or arrhythmia, bradycardia
Active respiratory disorder
Alcohol or substance use disorders
History of DBS or other brain surgery
Epilepsy
Pregnancy
B-Blockers, dopamine blocking agent, antiarrhythmic medication, acetylcholine esterase inhibitor, midodrine, florinef, droxidopa, or anticholinergic drugs

5. Randomization and masking

Randomization of the 35 subjects will be designed to yield an expected assignment ratio of 1:1 for taVNS and sham stimulation. Treatment assignments will be masked to the patients and to all study personnel with exception of PI and others vital to providing the actual treatment. Patients will be masked to transcutaneous stimulation of the auricular branch of the vagus nerve at the tragus, versus sham stimulation. Sham stimulation involves identical perceptual threshold finding and stimulation parameters as active stimulation, with the exception of stimulation target. Sham stimulation will be delivered to the left earlobe, a target

believed to have little to no vagal nerve innervation. A blinded MUSC Movement Disorder Neurologist will rate six videotaped MDS UPDRS examinations. Rater will be blinded to sham versus active stimulation, pre-stimulation versus post-stimulation state, and to the stimulation day of study.

6. Treatment plan

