Consented patient participants will be assigned a random *4-digit study ID number and blood serum samples will be drawn by appropriately trained staff. There will be two blood draws per patient; one baseline and one at the conclusion of the study. Blood samples will be delivered to [name] lab as soon as possible, following all standard procedures for safe transportation and storage. [name] personnel will be blinded to sample name, diagnosis, and all other personal identifiers.

A paper log containing names and corresponding study IDs will be kept in a locked room and locked filing cabinet in the Movement Disorder Program Suite. This room will not be accessed by patients, and is separate from the room where patient evaluations are performed.

10. Follow up visit

Visit 11 (Safety follow up visit) 6-14 days after visit 10, we will check for any adverse events that might have occurred since the last stimulation session, just as we have with every visit.

11. Outcomes Assessments

11.1 Primary outcome: Clinically meaningful treatment difference of the MDS - UPDRS motor section

Videotaped, modified UPDRS evaluations have been established as a reliable research method with very high correlation to full UPDRS assessments.¹⁴ The UPDRS is modified due to the fact rigidity is not assessed by a rater watching a videotaped examination.

The six motor examinations will be compared for both acute as well as cumulative effects of stimulation:

- 1) Visit 1 pre-stimulation comparison to visit 1 post stimulation: acute effect
- 2) Visit 5 pre-stimulation comparison to visit 5 post stimulation: acute effect
- 3) Final Visit 10 pre-stimulation comparison to Visit 10 post stimulation: acute effect
- 4) Visit 5 pre stimulation comparison to Visit 10 pre-stimulation: subacute effect
- 5) Visit 1 pre-stimulation comparison to final Visit 10 pre-stimulation: subacute effect
- 6) Visit 1 pre-stimulation comparison to final Visit 10 post-stimulation: subacute effect

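### The schedule of activities contradicts the text on Visit 10: the third pre-stimulation MDS-UPDRS is marked at follow-up and the second blood draw is not marked

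*Combined protocol and SAP*

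**What the plan says.** **Schedule of activities (section 3).** The table has nine visit columns: screening, Visit 1, Visits 2-4, Visit 5, Visit 6, Visits 7-8, Visit 9, Visit 10 and follow-up. The row "Pre-stim MDS UPDRS" has marks at Visit 1, Visit 5 and follow-up. The row "Post-stim MDS UPDRS" has marks at Visit 1, Visit 5 and Visit 10. The blood-draw row has one mark, at screening.

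**Text.**
- Sections 3 and 8 both give Visit 10 an off-medication "motor evaluation pre/post stimulation as at visit 1, in addition to the stimulation session. Repeat blood draw".
- Section 9, repeated in section 14.6, says: "There will be two blood draws per patient; one baseline and one at the conclusion of the study".
- Section 11.2 times the second serum measurement after the last stimulation session.
- Section 11.1 says "The six motor examinations will be compared for both acute as well as cumulative effects of stimulation" and lists six comparisons. Three of them use the Visit 10 pre-stimulation examination: "Final Visit 10 pre-stimulation comparison to Visit 10 post stimulation: acute effect", "Visit 5 pre stimulation comparison to Visit 10 pre-stimulation: subacute effect" and "Visit 1 pre-stimulation comparison to final Visit 10 pre-stimulation: subacute effect".
- Sections 10 and 11.3 describe the follow-up visit as a check for adverse events with a physical examination. They mention no stimulation and no motor examination.

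**The concern.** A schedule of activities is an instruction about what to do at each visit, and here it disagrees with the text on two procedures at the last treatment visit. A pre-stimulation examination at follow-up would precede nothing, because no stimulation is given there.

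What is at stake is the separation of cumulative from acute effect. Comparison 5 (Visit 1 pre to Visit 10 pre) is the only listed baseline-to-end comparison that leaves out the same-day effect of the last session, since comparison 6 ends after that session. Without a second blood sample, the serum hypotheses of Aim 4 and the serum effect sizes of section 12.2 have no change to analyse. Neither a missed Visit 10 examination nor a missed sample can be obtained later.

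The slip would also be hard to spot from totals. The table still yields three pre- and three post-stimulation examinations, which matches the six recordings that section 5 says the blinded rater will score. Scoring is left until the study is complete, so a recording from the wrong visit might be noticed late.

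**Working it through.** No sample-size or test arithmetic applies. The check maps each table row to its visits and asks which planned comparisons have both of their examinations.

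**1. Reading the rows.** Of the eight rows parsed column by column, each has nine visit cells.

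| Row | Marks in the table | What the text says |
|---|---|---|
| Pre-stimulation MDS-UPDRS | Visits 1, 5, follow-up | Visits 1, 5, 10 |
| Post-stimulation MDS-UPDRS | Visits 1, 5, 10 | Visits 1, 5, 10 |
| Blood draw | Screening | Screening, Visit 10 |
| Cognitive battery | Screening, Visit 9 | Screening, Visit 9 |
| C-SSRS | Screening, Visits 6, 9 | Three visits (count only, section 11.3) |
| Physical examination | Screening, follow-up | Two visits, one of them follow-up (section 11.3) |
| Pupillometry | Visit 1 | Visit 1 (section 8) |
| Adverse events | Visit 1 to follow-up | Every stimulation visit and follow-up |

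The saccade row (Visit 6) and the stimulation row (Visits 1 to 10) also agree with the text. Only the pre-stimulation and blood-draw rows disagree.

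**2. Motor comparisons.** The text provides pre and post examinations at three visits: 3 × 2 = 6. The table also provides 3 + 3 = 6, but one is at follow-up instead of Visit 10 pre-stimulation.

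| Section 11.1 comparison | Under the text | Under the table |
|---|---|---|
| 1. Visit 1 pre to Visit 1 post | yes | yes |
| 2. Visit 5 pre to Visit 5 post | yes | yes |
| 3. Visit 10 pre to Visit 10 post | yes | no |
| 4. Visit 5 pre to Visit 10 pre | yes | no |
| 5. Visit 1 pre to Visit 10 pre | yes | no |
| 6. Visit 1 pre to Visit 10 post | yes | yes |

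The text supports 6 of 6 and the table supports 3 of 6, so 6 − 3 = 3 are lost.

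**3. Serum markers.** A change from baseline needs two samples. The text gives two and the table gives one, so change is lost for 3 of 3 markers (BDNF, TNF-alpha, IL-6).

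**4. What does not depend on these cells.**
- Resting pupil diameter, also an Aim 4 biomarker, is recorded during stimulation and is marked at Visit 1.
- The section 12.1 contrast is a final post-stimulation score minus baseline. Read as Visit 10 post minus Visit 1 pre, it is comparison 6, and both examinations are marked.

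**The case against.** **The mismatch may come from the PDF reading.** The evidence is the position of marks in a machine-read table. One discrepancy is a mark one column to the right, the other a missing mark, and a damaged reading could produce both. The pre-stimulation row keeps the expected number of marks. For C-SSRS, and in part for physical examination, the text confirms only a count and so does not validate the columns. This stands as a caveat. It is not the likelier explanation, because the post-stimulation, cognitive-battery, saccade, stimulation and adverse-event marks all fall where the text puts them.

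**The text is clear and repeated.** Sections 3 and 8 each state the Visit 10 procedures, and sections 9, 11.1, 11.2 and 14.6 support them. This is a single-site pilot, and nothing in the documents says that staff work from the table alone. This also stands: the loss is conditional, and a reader who inferred that the data will be missing would go beyond the documents.

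**The primary analysis is not touched.** A reader might infer from three lost comparisons that the primary test is at risk. The documents do not support that, since the section 12.1 contrast makes no use of the Visit 10 pre-stimulation examination. One qualification is needed: section 12.1 refers to a final on-medication visit whereas Visit 10 is off medication, so identifying the contrast with comparison 6 is an assumption.

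**A follow-up motor examination may be deliberate.** Sections 6.3 and 14.5 list MDS-UPDRS among the safety assessments. But sections 10 and 11.3 do not include it in the follow-up visit, and adding it to the text's six would make seven.

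**Conclusion.** The point holds as an internal inconsistency between the schedule and the text. It is not a flaw in the design, which the text states consistently. Followed literally, the table would cost comparisons 3, 4 and 5 of section 11.1 (half of those listed) and all serum biomarker change.

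A reader might go further and conclude that all biomarker change data would be lost. The documents do not support that, because pupil diameter is unaffected. The serum markers also belong to an aim labelled exploratory in section 2, although sections 11.2 and 12.2 treat them as secondary.

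The conclusion assumes that the table was read correctly from the PDF, and the loss occurs only if staff follow the table where it differs from the text. The survival of the primary contrast assumes that section 12.1 means Visit 10 post-stimulation minus Visit 1 pre-stimulation. The correction is worth making because the loss would be irrecoverable and the change costs almost nothing.

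**What to change.** First check the two rows in the original document, to rule out damage in the PDF reading. If the marks are as described, reconcile the schedule with sections 3, 8, 9, 10 and 11:

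- Mark the third pre-stimulation MDS-UPDRS at Visit 10 and remove the mark at follow-up.
- Add a blood-draw mark at Visit 10, with a note that the sample is taken after the session, as section 11.2 has it.
- If a follow-up motor examination is intended, keep it in a separate row not labelled pre-stimulation, describe it in sections 10 and 11 with its medication state and purpose, and correct the count of six examinations in sections 5 and 11.1.

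The basic correction is three table cells: one mark removed and two added. It needs no change to sample size, visits or analysis.

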6.3 Management and reporting adverse events

Management: All adverse events occurring after randomization and during the treatment period, regardless of adherence to study treatment, will be recorded at all visit contacts. Procedures will be promptly discontinued if the participant reports significant distress that does not improve with time or intractable side effect of taVNS.

Importantly, all of these methods have been done before, and published by our and other groups in adults, and we believe these extra precautions will assure the safety and well-being of any participants enrolled.

Patients and caregivers will be asked about visits to doctors, healthcare providers, and emergency departments for other than routine care. The Principal Investigator (PI) will be responsible for monitoring the safety of patients, as well as for appropriate medical care of patients during the study in connection with study procedures.

Safety assessments will include physical exam, vital signs (heart rate primary measure, with additional blood pressure, respiratory rate and pulse oximetry monitoring), MDS UPDRS examinations and Cognitive examinations, Columbia- Suicide Severity Rating Scale

(C-SSRS), monitoring of adverse events, and monitoring and maintenance of concurrent medication records.

Reporting:

The supervising Institutional Review Board (IRB) will be notified of adverse events, risks, or unanticipated problems according to their reporting requirements. If any adverse events are noticed which are not described in the consent or are serious, we will inform the IRB before continuing with the next enrolled subject. Data collected regarding serious adverse events will include the treatment provided, outcome, and presumed relationship to study stimulation and will be updated as new information becomes available; a narrative description also will be provided.

Data Safety Monitoring Board will be utilized. See full description below; An independent review committee charged to monitor the conduct of the protocol to ensure the safety of participants and the validity and integrity of the data.

7. Screening and Baseline visit

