13.2 Quality assurance monitoring

The best assurance device is quality-conscious personnel. PI will meet regularly with the research staff, review data collected, and review consent documents for accuracy and completeness. In addition, staff will be reminded of their responsibilities in adhering to high ethical standards, in protecting the privacy of trial participants and confidentiality of records, and in collecting accurate data. They will be reminded to make known to proper authorities any suspicious or wrongful actions in relation to the study. Each member of the research group will sign a statement indicating knowledge and understanding of the above and to disclose potential conflicts of interest. The next best set of assurances lies in the use of design strategies that protect the results from treatment-related biases. This includes random assignment of patients to active treatment or placebo, and masked data collection and outcome assessment. Assurances also depend on the documents, and procedures used for data collection and monitoring.

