14.6 Confidentiality of patient data

We will keep all patient and caregiver data in a secure locked office, in a locked cabinet and away from patient access areas. Names, addresses, and other such personal data will not be part of the REDcap database.

Study data will be collected and managed in a REDCap database (Research Electronic Data Capture). The database will be managed by a data manager from the MUSC SCTR (SCTR= South Carolina Clinical and Translational Research Institute, that provides infrastructure for enhancing clinical research studies). The PI will perform error checking, and ensure that human subjects data is de-identified, that it meets all regulatory requirements, and that it is stored and backed-up in a secure fashion. REDCap is a secure, web application designed to support data capture for research studies, providing user-friendly web-based case report forms, real-time data entry validation, audit trails and a de-identified data export mechanism to common statistical packages. The database is hosted at the MUSC Datacenter. The system is protected behind a login and Secure Sockets Layer encryption.

Patient video will be collected within the secure “BOX” password protected network storage application that is MUSC IT security approved for patient PHI. There will be no end user device storage of PHI during collection or access. Single sign-in is required for access on any end user device. Folder access will be managed by the physician obtaining the video, the PI, and the blinded Movement Disorder Neurologist. Only after individual login will these key physicians be able to discover the study folder. Data collected from study evaluations and interviews will be identified only by study ID codes, which will be the patient ID and 4-letter code assigned at eligibility evaluation.

Consented patient participants will be assigned a random *4-digit study ID number and blood serum samples will be drawn by appropriately trained staff. There will be two blood draws per patient; one baseline and one at the conclusion of the study. Blood samples will be delivered to [name] lab as soon as possible, following all standard procedures for safe transportation and storage. [name] personnel will be blinded to sample name, diagnosis, and all other personal identifiers.

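### The PI knows each participant's arm yet reviews and error-checks the study data, so values can be queried or corrected with the arm known

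*Combined protocol and SAP*

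**What the plan says.** Section 5 sets the masking rule: "Treatment assignments will be masked to the patients and to all study personnel with exception of PI and others vital to providing the actual treatment". The PI is thus outside the mask by design, together with those who deliver stimulation.

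Other sections then give the PI tasks that touch the data:

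- Section 14.6: "The PI will perform error checking, and ensure that human subjects data is de-identified". The same section says that a data manager from a separate institute at the university manages the REDCap database, and that REDCap offers entry validation and audit trails.
- Section 13.2: "PI will meet regularly with the research staff, review data collected, and review consent documents for accuracy and completeness".
- Section 6.3: "The Principal Investigator (PI) will be responsible for monitoring the safety of patients, as well as for appropriate medical care of patients during the study". For serious adverse events the data include the "presumed relationship to study stimulation", but the section does not say who makes that judgement.

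Section 13.2 also lists, among the design features that guard against bias, "masked data collection and outcome assessment". Section 13.1 says that only the DSMB sees partially unblinded summaries of adverse events and outcomes, and describes the study team as partially blinded for parts of the study.

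No section says that data checks are made without the arm, or that the database is locked before allocation is joined to it.

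**The concern.** Error checking involves judgement. Someone decides which values look implausible, which source records to pull, and whether an entry is corrected, set to missing or left alone. If that person knows the arm, these decisions can differ between arms without any intent. A poor cognitive score on active stimulation may be questioned where the same score on sham is accepted.

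At stake is the credibility of the between-arm comparisons on cognition (Aim 2) and tolerability (Aim 3), in a trial small enough for a few altered values to matter. Section 12.2 adds to this: it allows outlier screening and transformation where indicated, without stating a rule or saying who applies it. The PI's access also weakens the claim in 13.2, which readers of the results would otherwise rely on.

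**Working it through.** The plan gives no figure on this point to reproduce, so the check sets the sections side by side.

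1. **Does the PI know the arm?** Yes. Section 5 exempts the PI by role.

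2. **Does the PI handle participant-level data?** Yes. Section 14.6 assigns error checking and section 13.2 assigns review of collected data. Neither limits this to data stripped of arm. De-identification, which 14.6 also requires, removes names but does not hide the arm from someone who already knows it.

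3. **Is this consistent with 13.2 and 13.1?** The 13.2 protection can be met at the point of collection (masked staff) and of scoring (masked rater). It is not met at review and checking, which the same section gives in part to the PI. Section 13.1 reserves partially unblinded comparisons for the DSMB, but a PI who knows the arms and reviews the data can make the same comparison informally.

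4. **Which data are exposed?**
   - *Primary motor score.* Sections 5 and 8 have a neurologist score all videos at study completion, unaware of arm, of whether the recording precedes or follows stimulation, and of the day. A disputed score can be checked against the stored video. The remaining exposure is a query after entry.
   - *Cognitive battery.* Given at screening and visit 9 (section 3), with no recording or second scoring described. Section 12.2 averages the tests into a composite, so changing or removing one component moves the composite.
   - *Patient-reported scales.* The respondent is masked, but entered values are open to query.
   - *Vital signs.* Less open to judgement at measurement, but still open to selective query.
   - *Adverse events.* All are recorded at every contact (6.3), but entries can be queried, and the PI is also the safety lead.
   - *Serum markers.* Section 9 blinds laboratory staff to sample identity, so exposure begins only when results are returned.

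5. **Do the stated safeguards close the gap?** An audit trail shows which edits were made. It does not stop a query being raised with the arm in mind, and it does not show why one value was questioned and a similar one was not. The DSMB sees summaries prepared by the coordinator (13.1), which come after any correction.

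6. **Who assesses relatedness?** Section 6.3 asks for it for serious events and names nobody. The one safety lead it names is unmasked.

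**The case against.** The best case for the plan runs as follows. In a single-site pilot, the PI may have to be unmasked to deliver treatment. The error-checking duty in 14.6 sits in a sentence about de-identification, regulatory requirements and secure storage, and nothing gives the PI authority to change scores. The primary outcome is well protected by the masked video rater. REDCap logs edits, and under 13.1 the DSMB asks the database manager whether quality control is working. The 13.2 wording can be read as covering only masked collecting staff and the masked rater.

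Most of this stands as a limit on the concern. It places the exposure mainly outside the primary motor score and makes edits traceable. It does not answer the central point: error checking and data review are assigned to an unmasked person, and no text keeps the arm out of those steps.

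A reader might go further and infer that the PI judges adverse events with the arm known, tilting Aim 3 towards no difference. The documents do not support that. Section 6.3 names no assessor, asks for relatedness for serious events only, records all events regardless, and describes no severity grading. Section 11.3 treats tolerability as mean change plus documentation of events, and section 12 plans no between-arm safety test.

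Nor can a size be attached by counting re-judged events. With 15 per arm (sections 3 and 7.1), one event is 1/15 = 6.7 percentage points and two are 2/15 = 13.3. With 35 enrolled (sections 2, 5 and 12.3), the average arm is 35/2 = 17.5, giving 1/17.5 = 5.7 and 2/17.5 = 11.4. These figures need a related-event rate as an endpoint, and the plan defines none. It would also be wrong to call any bias undetectable, given the audit trail and the stored videos.

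**Conclusion.** The concern holds as a weakness in data handling. The plan leaves the PI unmasked and gives that person error checking and review of the data, which is inconsistent with the protections described in 13.2 and 13.1. The cognitive, patient-reported, vital-sign and adverse-event data are the main exposure; the primary motor score is largely protected.

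The size of any bias cannot be derived from the documents, and nothing in them shows that bias has occurred. The conclusion assumes that error checking involves looking at individual values, and that the PI can link study IDs to known arms. The unnamed assessor of serious-event relatedness is a smaller gap of the same kind.

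**What to change.** In 14.6 and 13.2, assign error checking and query generation to the data manager already named, working without the allocation. Add that queries are resolved and the database locked before allocation is merged for analysis. The PI keeps responsibility for patient care and regulatory oversight. With this change, the statement in 13.2 would describe the checking step as well as collection and rating.

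As a secondary step, state in 6.3 that the presumed relationship of serious adverse events is recorded by an investigator masked under section 5, where one is available. Section 14.3 mentions a sub-investigator and co-investigators but does not say whether any of them is masked, so this must be settled first.

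The cost is a few sentences in 14.6, 13.2 and 6.3. The data manager takes on the query work and must be kept from the allocation, and a masked investigator must be available when a serious event occurs. The main change needs no new staff; the secondary one depends on finding a masked investigator in the existing team.
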